4.2.2 Secondary Endpoints

a. Efficacy

- Proportion of samples at each time point in which [REDACTED] can be detected by molecular diagnosis
- Proportion of samples at each time point in which *T. rubrum* can be detected by molecular diagnosis
- Relative abundance of *T. rubrum* at each time point
- Change in abundance of *T. rubrum*
- Changes in the signs and symptoms of *T. pedis*
- Change from dermatophyte culture positive to culture negative
- Change from KOH positive to KOH negative

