6.5.2 All Other Visits

Study visit assessments will be conducted as presented in Tables 2 and 3.

a. Baseline (Day1) visit:

For subjects who did not have a screening washout period will have the following tasks completed at baseline Day 1:

1. Informed consent.
2. Record demographics.
3. Review of Inclusion/Exclusion Criteria.
4. Medical history.
5. Concomitant medication.
6. T. pedis ISGA of each web space on both feet.
7. T. pedis signs and symptoms.
8. Classification toe web space. As not all web spaces are equally affected and the act of collecting samples from a web space could affect the laboratory results. Web spaces on both feet will be classified based on the ISGA as clear, almost clear, mild T. pedis, moderate T. pedis, severe T. pedis. In addition, one representative web space classified

as moderate will be designated as the target sampling web space. Representative web space should be marked on each subject's paperwork for reference.

9. Signs and symptoms of local tolerability of the areas other than the web spaces.
10. Collect sample for onsite KOH from the target sampling web space.
11. Collect sample for reference mycology laboratory from the target sampling web space.
12. Collect an e-swab from the target sampling web space.
13. Obtain digital photograph of the target sampling web space.
14. Assigned test article will then be applied to both feet. Approximately 0.5 ml of the test article will be applied to each foot spreading the test article over all web spaces, on and around all toe nails, the entire plantar and lateral aspects of the foot.
15. Record any adverse event, if any.

16. One hour after application of the test article, the following activities will be done:

- a. E-Swab from an affected web space other than target sampling web space.
- b. Signs and symptoms of local tolerability of the areas other than the web spaces.
- c. Record adverse event, if any.
- d. Give an appointment for Day 2 visit.

For subjects **who had a screening** visit prior to a baseline visit before the test article is applied will have the following tasks completed:

1. Review of Inclusion/Exclusion Criteria.
2. Update Medical History.
3. Concomitant medications.
4. Record Adverse events, if any.
5. T. pedis ISGA of each web space on both feet.
6. T. pedis signs and symptoms.

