7. Classification toe web space. As not all web spaces are equally affected and the act of collecting samples from a web space could affect the laboratory results. Web spaces on both feet will be classified based on the ISGA at clear, almost clear, mild T. pedis, moderate T. pedis, severe T. pedis. In addition, one representative web space classified as moderate will be designated as the target sampling web space.
8. Signs and symptoms of local tolerability of the areas other than the web spaces.
9. Collect sample for reference mycology laboratory from the target sampling web space
10. Collect an e-swab from the target sampling web space.
11. Obtain digital photograph of the target sampling web space.
12. Assigned test article will then be applied to both feet. Approximately 0.5 ml of the test article will be applied to each foot spreading the test article over all web spaces, on and around all toe nails, the entire plantar and lateral aspects of the foot

13. One hour after application of the test article, the following activities will be done:

- a. E-Swab from an affected web space other than target sampling web space.
- b. Signs and symptoms of local tolerability of the areas other than the web spaces
- c. Record adverse event, if any.
- d. Given an appointment for Day 2 visit.

Detailed instruction for sample collection and processing are in the Study Operation Manual, provided separately.

Day 2 Approximately 24 hours after the test article was applied:

1. Concomitant medications.
2. Adverse events.
3. T. pedis ISGA of each web space on both feet.
4. T. pedis signs and symptoms.
5. Signs and symptoms of local tolerability of the areas other than the web spaces.
6. Collect an e-swab from an affected but previously not sampled web space. If none available collect e-swab from an unaffected but previously not sampled web space.
7. Give subject appointment for Day 3 visit.

Detailed instruction for sample collection and processing are in the Study Operation Manual, provided separately.

Day 3 Approximately 48 hours after the test article was applied:

1. Concomitant medications.
2. Adverse events.
3. T. pedis ISGA of each web space on both feet.
4. T. pedis signs and symptoms.
5. Signs and symptoms of local tolerability of the areas other than the web spaces.
6. Collect an e-swab from an affected but previously not sampled web space. If none available collect e-swab from an unaffected but previously not sampled web space.

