6.11 General Statistical Considerations

As this is an open label safety and tolerability trial all of the collected data will be presented in listings, tables, and figures in a descriptive fashion.

Primary Objective:

Evaluate the safety and tolerability of DBI-001 in patients with Tinea pedis

Secondary Objective:

Evaluation of presence or persistence of [REDACTED] of DBI-001 following a single application of DBI-001.

Effect of a single application of DBI-001 on the abundance of *T. rubrum*

Effect of a single application of DBI-001 on the signs and symptoms of interdigital T. pedis.

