6.12 Analysis of Data for Objectives

- a. Primary Objective: Evaluation of presence or persistence of [REDACTED] following a single application of DBI-001.
- b. Secondary Objective: Effect of a single application of DBI-001 on the abundance of *T. rubrum*.
- c. Exploratory Objectives: Effect of a single application of DBI-001 on the signs and symptoms of interdigital T. pedis.

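### The T. rubrum endpoints name no web space or reference visit, so a difference from Baseline at 1 hour, Day 2 or Day 3 mixes sampling site with time

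*Combined protocol and SAP*

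**What the plan says.** Section 6.5.2 and Table 3 (in 6.6.4) agree on where the e-swab is taken:

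- Baseline and Days 7, 14 and 28: the target web space.
- 1 hour after application: an affected web space other than the target.
- Days 2 and 3: an affected web space not yet swabbed. The fallback reads: "If none available collect e-swab from an unaffected but previously not sampled web space".

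The step in 6.5.2 that classifies the web spaces gives its reason: "As not all web spaces are equally affected and the act of collecting samples from a web space could affect the laboratory results".

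Three of the secondary endpoints in 4.2.2 use these swabs to measure T. rubrum:

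- The first concerns detection and is worded "Proportion of samples at each time point in which *T. rubrum* can be detected by molecular diagnosis".
- The second concerns the level found and is worded "Relative abundance of *T. rubrum* at each time point".
- The third, listed as an item of its own, is worded "Change in abundance of *T. rubrum".

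None of the three names a web space, and the last names no reference visit. Section 6.12 restates the objective without an estimator. Section 6.13 includes every treated subject. Section 6.11 says that "all of the collected data will be presented in listings, tables, and figures in a descriptive fashion".

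**The concern.** The collection plan changes site between visits, but the endpoints treat the visits as one series. A table or curve of T. rubrum by time point would start in the target space, move to other spaces for three visits, and return to the target space from Day 7. The protocol itself says that web spaces differ in how badly they are affected, so a step in that series between Baseline and Day 3 could come from the change of space alone.

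The trial is open label with no control arm. A concurrent control sampled on the same rotation would carry the same site difference and allow it to be removed; here nothing does. What is at stake is the secondary objective on T. rubrum abundance, in the days just after application, where an early effect of the product would be looked for.

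**Working it through.** The plan has no figure to reproduce: 6.14 states that no assumptions were made in choosing the sample size. The check sets the swab schedule against the endpoints.

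**Sites by time point (6.5.2 and Table 3)**

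| Time point | Space swabbed | Same space as the Baseline swab? |
|---|---|---|
| Baseline | target | reference |
| 1 hour | affected, not target | no |
| Day 2 | new affected, else new unaffected | no |
| Day 3 | new affected, else new unaffected | no |
| Day 7 | target | yes |
| Day 14 | target | yes |
| Day 28 | target | yes |

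There are 7 time points: 4 at the target and 3 elsewhere. Post-dose time points: 7 − 1 = 6. Those with no pre-dose swab from the same space: 3 of 6.

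This count takes Table 3 literally, with the target as the only space swabbed before dosing. Section 6.6.4 also says that a subject with both feet affected is sampled on each foot. If that gives a second Baseline swab on the other foot, the 1-hour swab might come from a space already swabbed. On Days 2 and 3 the rule to use a space not yet swabbed excludes this.

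**What an early difference contains.** Let m(s, t) be the mean T. rubrum level in space s at time t. For a visit at another space:

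m(other, t) − m(target, 0) = [m(other, t) − m(other, 0)] + [m(other, 0) − m(target, 0)]

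The first bracket is change over time in one space. The second is the pre-dose difference between spaces. Because m(other, 0) is not measured under Table 3, the two cannot be separated. On Days 7, 14 and 28 the space is the target, so the second bracket is m(target, 0) − m(target, 0) = 0.

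**Can the sign of the second bracket be derived?** No. Section 6.5.2 makes a moderate space the target, so another affected space may be milder or severe; the fallback is an unaffected space. The documents give no T. rubrum detection rate or abundance by severity. The bracket is zero only if the spaces do not differ or the differences cancel.

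**Is the fallback likely to be used?** Without repeats, the schedule uses 1 (target) + 1 (1 hour) + 1 (Day 2) + 1 (Day 3) = 4 distinct spaces by Day 3. Eligibility (6.1, item 6) rests on one target lesion and sets no minimum number of affected spaces. For a subject sampled on one foot only, with one swab per visit:

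- fewer than 4 affected spaces on that foot: the Day 3 swab is from an unaffected space;
- fewer than 3: the Day 2 swab is too;
- only the target affected: no 1-hour site is named.

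This does not extend to subjects swabbed on both feet, whose spaces would have to be counted per foot. The documents do not say how many subjects fall in each group.

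**The case against.** The strongest reply is that the plan prescribes no biased comparison. The change endpoint is a separate item from the two reported by time point, and nothing says to subtract the target Baseline value from a swab of another space. Comparing Baseline with Days 7, 14 and 28 is an equally open reading. All output is descriptive, a proportion at a given visit is still a true description of the swabs taken, and Table 3 fixes target or non-target for each visit, so a label on the output would do. The rotation is also deliberate, because sampling may itself alter the result.

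Much of this stands. The change endpoint is undefined, not wrongly defined, and the rotation should stay. But the two series by time point, followed as worded, do place different spaces on one time axis, and no text asks for the label.

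Two further inferences are tempting and go too far:

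- *That the swabbed space cannot be traced.* Section 6.6.4 asks the CRF for left or right foot, but does not say that nothing else is recorded, and the CRF is not among the documents. The rule to use a space not yet swabbed requires someone to know which were swabbed; 5.2 lists sample labels and logs, and 9.7 requires records of all samples. None of this proves that the web space is recorded, so it has to be confirmed.
- *That the 6.6.4 table, which gives no microbial sampling for a Clear grade, contradicts the unaffected fallback.* Its column heading refers to the web space, but its entries about the contralateral side work at the level of the foot. Read that way there is no conflict. The wording is ambiguous.

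The Study Operation Manual, which was not available, could settle both, as well as the missing 1-hour site. It is cited for visit procedures and for sample collection and processing, not for endpoint definitions, so it is not a likely home for the missing analysis rule.

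**Conclusion.** The point holds within limits. For T. rubrum at 1 hour, Day 2 and Day 3 (3 of 6 post-dose time points, with Table 3 read literally), a difference from Baseline cannot be separated from a difference in web space. The endpoints and analysis sections contain no rule that prevents this.

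A reader might infer that the site change must produce a spurious fall in T. rubrum. The documents do not support a direction or a size. Nor do they support a wider reach: the same-site comparison of Baseline with Days 7, 14 and 28, the primary tolerability endpoint and the escalation decisions are not affected. No defect is claimed for detection of the applied organism.

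The conclusion rests on the protocol's own statement that web spaces are unequally affected, and on the absence of a control arm. Severity is minor to moderate: the objective is secondary and descriptive, but its early results would not be interpretable if tabulated as the endpoints are worded.

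**What to change.** In 4.2.2 and 6.12, add two sentences to this effect:

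- T. rubrum change from baseline, and the detection and abundance series over time, are reported for the target web space only (Baseline, Days 7, 14 and 28).
- T. rubrum results at 1 hour, Day 2 and Day 3 are presented separately, labelled by the web space swabbed and by whether it was affected or unaffected at baseline, with no change calculated from the target Baseline value.

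The label is feasible because 6.5.2 grades every web space by ISGA before dosing; state which grades count as affected.

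Make sure that foot and web space are recorded for every e-swab, after checking whether the CRF or the Study Operation Manual already provides for this. As secondary wording points, reconcile the Clear row of the 6.6.4 table with the unaffected fallback, and state the 1-hour site when no other space is affected. If the manual covers these, cite it in 6.6.4.

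The swab schedule and rotation do not change. The cost is two sentences, at most one CRF field per swab, and some wording in 6.6.4. There are two downsides. No estimate of T. rubrum change would exist before Day 7. The target series may also carry an effect of repeated sampling: that space has been sampled on 1, 2 and 3 earlier scheduled days (Baseline; plus Day 7; plus Day 14) before the Day 7, 14 and 28 swabs, and on one more if a separate screening KOH came from the same space. State this as a limitation of the series.

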6.6 Study Specific Procedures

6.6.1 Grading of signs and symptoms of T. pedis

Will be graded as follows:

Fissuring/Cracking score:

0=none (complete absence),
1=mild (slight)

2=moderate (definitely present)
3=severe (marked, intense)

Erythema score:

0=none (complete absence)
1=mild (slight),
2=moderate. (definitely present)
3=severe (marked, intense)

Maceration score:

0=none (complete absence)
1=mild (slight)
2=moderate (definitely present)
3=severe (marked, intense)

Scaling score:

0=none (complete absence)
1=mild (slight)
2=moderate (definitely present),
3=severe (marked, intense)

Pruritus score:

0=none (complete absence)
1=mild (slight)
2=moderate (definitely present)
3=severe (marked, intense)

Burning/Stinging score:

0=none (complete absence)
1=mild (slight)
2=moderate (definitely present),
3=severe (marked, intense)
Composite (total) signs and symptoms score

6.6.2 T. pedis Investigator's Static Global Assessment (ISGA)

Clear - possible faint erythema and a hint of scale

Almost clear - slight scale and minimal erythema

Mild - definite scale and erythema but no maceration, cracking or fissuring

Moderate - definite (mild to moderate) scale, erythema, maceration, and cracking or fissuring

Severe - at least moderate or severe scale, erythema, maceration, and cracking or fissuring

6.6.3 Local Tolerability for Areas Not Affected by T. Pedis

Local tolerability for areas to which the test article is to be applied but without T. pedis such as the unaffected web spaces on and around the toes, toe nails, the plantar and lateral aspects of the foot tolerability will be evaluated based on these signs and symptoms:

Pain/Burning: as reported by the subject as being the greatest intensity they have experienced within the last 24 hours at Baseline or since the last visit at subsequent visits.

0	None	No pain/burning
1	Mild	Slight burning/stinging sensation; not really bothersome
2	Moderate	Definite warm, burning/stinging that is somewhat bothersome
3	Severe	Hot burning/stinging sensation that causes definite discomfort and may interrupt daily activities and/or sleep

Pruritus: as reported by the subject as being the greatest intensity they have experienced within the last 24 hours at Baseline or since the last visit at subsequent visits.

0	None	No pruritus
1	Mild	Slight pruritus, not really bothersome
2	Moderate	Definite pruritus that is somewhat bothersome
3	Severe	Intense pruritus that may interrupt daily activities and/or sleep

Erythema: as assessed by the Investigator

0	None	No erythema present
1	Mild	Slight pink coloration
2	Moderate	Definite redness
3	Severe	Marked erythema, bright red to dusky dark red in color

Edema: as assessed by the Investigator

0	None	No edema
1	Mild	Slight, but definite edema
2	Moderate	Definite edema
3	Severe	Marked edema

Scabbing/Crusting: as assessed by the Investigator

0	None	No scabbing/crusting
1	Mild	Slight, but definite scabbing/crusting
2	Moderate	Definite scabbing/crusting
3	Severe	Marked scabbing/crusting

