Criteria for evaluation	
Evaluations will be made at Screening, Day 1 / Baseline prior to the application of the test article and then 1 hour after application and study days 2, 3+1, 7+/-1, 14+/-2 and 28+/-2.
 
Subjects will also be queried for adverse events starting after the informed consent is signed and all timepoints following application.
 
Primary:
 
• Signs and symptoms of irritation 
Secondary:
 
• Data listing showing duration of time over which DBI-001 can be detected by molecular diagnosis• Change in abundance of T. rubrum by molecular diagnosis• Changes in the signs and symptoms of T. pedis• Changes in the T. pedis ISGA• Frequency of conventional culture negative• Frequency of KOH negative
Statistical methods	Descriptive

Safety Results:	Dermal Safety and Tolerability: Tolerability will be evaluated through assessment of selected local signs and symptoms (pain / burning, pruritus, erythema, edema, and scabbing/ crusting). Any local skin reaction that requires use of a concomitant therapy or causing study drug interruption or discontinuation should be reported as an AE. The scales to be used for assessing local skin reactions follow
Adverse Events:	During the study, subjects will be assessed for the occurrence of new and ongoing AEs. Descriptions of AEs will include the dates of onset and resolution (if resolved), maximum severity, and seriousness, corrective treatment, outcome, and the Investigator's assessment of causality. AEs present at any visit will be followed to resolution (return to normal or to the baseline state) or until clinically stable as determined by the Investigator.

Efficacy Results:	
• Proportion of samples at each time point in which [REDACTED] can be detected by molecular diagnosis.• Proportion of samples at each time point in which T. rubrum can be detected by molecular diagnosis• Relative abundance of T. rubrum at each time point• Change in abundance of T. rubrum• Changes in the signs and symptoms of T. pedis• Changes in the T. pedis ISGA• Change from dermatophyte culture positive to culture negative• Change from KOH positive to KOH negative
--------------------------	--

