4. STUDY DESIGN AND ENDPOINTS

4.1 Description of the Study Design

A single center open label dose escalating study design will be used in a population of patients with interdigital *Tinea pedis*. Each subject will have a single application of approximately 0.5 ml of the test article applied to each foot covering the web spaces of both feet as well as the plantar and lateral aspect of both feet as well as on and around all toes and toe nails. The three test articles will be 10^6 CFUs/ml, 10^7 CFUs/ml, and 10^8 CFUs/ml. Each of the three groups will have 4 subjects. After the first cohort has completed their day 7 visits and if no significant tolerability of safety issues is identified the second cohort will be enrolled. After the second cohort has completed the day 7 visits and if no significant tolerability or safety issues are identified the third cohort will be enrolled.

Evaluations will be followed according to Table 2 Schedule of Events for Subjects. At all evaluations, signs and symptoms of application site reactions (local tolerability at sites unaffected by *T.pedis* interdigital) will be recorded. At baseline, days 2, 3 (+1), 7 (+/-1), 14 (+/-2), and 28 (+/-2), the signs and symptoms of *T. pedis* will be recorded. The investigators static global assessment (ISGA) of the interdigital *T. pedis* will be recorded at baseline, days 2, 3(+1), 7 (+/-1), 14 (+/-2), and 28 (+/-2). Subjects will also be queried for adverse events during their follow up visits or by self-reporting while on study until Day 28.

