4.2 Study Endpoints

4.2.1 Primary Endpoints

a. Safety

- Tolerability will be evaluated through assessment of selected local signs and symptoms (pain / burning / stinging, pruritus, erythema, edema, and scabbing / crusting). Any local skin reaction that requires use of a concomitant therapy or study discontinuation should be reported as an AE on the Case Report Forms.

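### Burning and pruritus are recalled over 24 hours at Baseline but over about 4, 7 and 14 days at Days 7, 14 and 28, which can inflate these two scores relative to baseline with no product effect

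*Combined protocol and SAP*

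**What the plan says.** Section 4.2.1 sets the primary endpoint: "Tolerability will be evaluated through assessment of selected local signs and symptoms". Five items are named: pain/burning/stinging, pruritus, erythema, edema and scabbing/crusting. Section 6.6.3 defines their 0-to-3 scales and applies them to "areas to which the test article is to be applied but without T. pedis".

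In that section, pain/burning and pruritus are reported by the subject as the "greatest intensity they have experienced within the last 24 hours at Baseline or since the last visit at subsequent visits". The other three are rated by the investigator, for example "Erythema: as assessed by the Investigator", with no recall period.

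The Synopsis schedules evaluations at Screening, at Baseline, 1 hour after application and on "study days 2, 3+1, 7+/-1, 14+/-2 and 28+/-2". Section 4.1 has tolerability recorded throughout: "At all evaluations, signs and symptoms of application site reactions". Section 6.5.2 places the Day 2 visit "Approximately 24 hours after the test article was applied".

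The study is open label with no control arm and 4 subjects per cohort. Section 6.11 plans descriptive presentation only. Nothing in the document adjusts for, or comments on, the unequal recall periods.

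**The concern.** A worst-of-period score depends on the length of the period. If symptoms come and go at a steady background level, a longer look-back is more likely to catch an episode. The Baseline look-back is 24 hours, while those at Days 7, 14 and 28 are several times longer. A table of these scores by visit can therefore show a rise after dosing that comes from the question and not from the product.

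With no concurrent control, nothing in the data separates the two, and each subject's own pre-dose score is the natural reference. The protocol itself uses baseline this way for adverse events. Section 8.2 counts a clinically relevant deterioration of an abnormal assessment against Baseline as an event, and the Synopsis follows events until they return to normal or to the baseline state. At stake is how two of the five primary items are read in very small cohorts.

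**Working it through.** The documents give no background symptom rate and no power calculation, so there is no plan figure to reproduce.

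**Step 1: recall length.** The nominal length is the visit day minus the previous visit day. The shortest is the earliest allowed day minus the latest allowed previous day; the longest is the reverse. Allowed days are 2; 3 to 4; 6 to 8; 12 to 16; 26 to 30.

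| Visit | Nominal | Shortest | Longest |
|---|---|---|---|
| Baseline | 24 hours | – | – |
| Day 2 | 2 − 1 = 1 day | 1 | 1 |
| Day 3 | 3 − 2 = 1 day | 3 − 2 = 1 | 4 − 2 = 2 |
| Day 7 | 7 − 3 = 4 days | 6 − 4 = 2 | 8 − 3 = 5 |
| Day 14 | 14 − 7 = 7 days | 12 − 8 = 4 | 16 − 6 = 10 |
| Day 28 | 28 − 14 = 14 days | 26 − 16 = 10 | 30 − 12 = 18 |

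At the 1-hour evaluation, recall since the pre-dose assessment is taken as about 1 hour, shorter than at Baseline.

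**Step 2: expected proportion scoring 1 or more with no product effect.** Let p be the chance of any symptom in 24 hours and ρ the day-to-day persistence (0 = independent days, 1 = the same state every day). Both are assumptions. Over k days,

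P = 1 − (1 − p)(1 − p(1 − ρ))^(k−1).

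For p = 5%:

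- ρ = 0: Day 7, 1 − 0.95^4 = 18.5%; Day 14, 1 − 0.95^7 = 30.2%; Day 28, 1 − 0.95^14 = 51.2%.
- ρ = 0.8, so p(1 − ρ) = 0.01: Day 7, 1 − 0.95 × 0.99^3 = 7.8%; Day 14, 1 − 0.95 × 0.99^6 = 10.6%; Day 28, 1 − 0.95 × 0.99^13 = 16.6%.
- ρ = 1: 5% at every visit.

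Other assumed rates, for Days 7, 14 and 28:

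| p (Baseline) | ρ = 0 | ρ = 0.8 |
|---|---|---|
| 0% | 0, 0, 0% | 0, 0, 0% |
| 1% | 3.9, 6.8, 13.1% | 1.6, 2.2, 3.5% |
| 10% | 34.4, 52.2, 77.1% | 15.3, 20.3, 30.8% |
| 20% | 59.0, 79.0, 95.6% | 29.2, 37.4, 52.9% |

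**Step 3: early time points, p = 5%.** At 1 hour, with a constant hourly chance, P = 1 − 0.95^(1/24) = 0.2%, below the 5% at Baseline. Day 2 and nominal Day 3 stay at 5%. If the Day 3 visit slips to Day 4 (k = 2), P is 9.8% (ρ = 0) or 5.9% (ρ = 0.8).

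**Step 4: one cohort of 4 at the Day 7 review, p = 5%.** The chance that at least one subject scores 1 or more is 1 − (1 − P)^4. This is 18.5% with a 24-hour window (P = 5%), 28% with P = 7.8%, and 56% with P = 18.5%.

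**Step 5: after the fix.** With 24-hour recall at every follow-up visit from Day 2, P = p at each of them under the same assumptions, and the rise due to recall length disappears.

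**The case against.** The strongest reply is that worst-since-last-visit is a sound safety choice, because a 24-hour question on Day 28 would miss a reaction in the preceding fortnight. That stands, and the fix keeps the item.

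Several other objections also stand and limit the point:

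- No change-from-baseline analysis of tolerability is specified; section 4.2.2 asks for change only in efficacy measures. The problem lies in how the scores will be read, not in a defined estimate.
- The Day 28 window does not contain the Baseline 24 hours, so an individual's later score can be lower. The inflation exists only in expectation.
- The scored skin is free of *T. pedis*, so background symptoms may be rare or absent. On the other side, pruritus/burning can count towards entry (section 6.1), and section 2.1 says the sampling detergent may irritate. A non-zero background is plausible but unquantified.
- A score of 1 is by definition hardly bothersome.
- Escalation rests on judgement after Day 7 (section 7.1), where recall is about 4 days. An error there overstates irritation.
- All cohorts share one schedule, so comparing cohorts at the same visit is not distorted by nominal recall length.

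A reader might infer that the primary tolerability scores as a whole must rise after dosing, or must peak at Day 28. The documents do not support this. Three of the five items have no recall period, the mismatch is downward at 1 hour and about nil at Days 2 and 3, and a real early reaction could peak well before Day 28.

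**Conclusion.** The point holds in a limited form. For pain/burning and pruritus, the change in recall period can inflate scores relative to baseline from Day 7 on with no product effect, and an uncontrolled study cannot tell this from a reaction to the product. It requires a background of symptoms that is non-zero and fluctuates from day to day.

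The size cannot be determined from the documents. At an assumed 5% daily rate, the Day 28 proportion ranges from 5% (full persistence) through 17% (persistence 0.8) to 51% (independent days). At a zero rate there is no effect. This is a cheap improvement to the measurement of two primary items, not a flaw that undermines the study.

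**What to change.** In section 6.6.3, keep the worst-since-last-visit rating as the safety record. At each follow-up visit from Day 2, also ask the same two items over the last 24 hours. In section 6.11, state that the 24-hour score is used whenever post-dose burning or pruritus is read against baseline or across visits. State also that worst-since-last-visit scores are tabulated with their recall length and are not read as change from baseline.

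The cost is two questions and a CRF line at each of five follow-up visits, or 2 × 5 × 12 = 120 extra answers in the whole study. No visit, procedure or sample is added.
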